## 7.2 Adverse Event Characteristics

- **CTCAE term (AE description) and grade:** The descriptions and grading scales found in the revised NCI Common Terminology Criteria for Adverse Events (CTCAE) version 5.0 will be utilized for AE reporting beginning April 1, 2018 (investigators may continue to collect and locally store AE data in CTCAE v4.0). All appropriate treatment areas should have access to a copy of the CTCAE version 5.0. A copy of the CTCAE version 5.0 can be downloaded from the CTEP web site [http://ctep.cancer.gov/protocolDevelopment/electronic\\_applications/ctc.htm](http://ctep.cancer.gov/protocolDevelopment/electronic_applications/ctc.htm).
- **For expedited reporting purposes only:**
  - AEs for the agent that are ***bold and italicized*** in the CAEPR (*i.e.*, those listed in the

SPEER column, Section 7.1.1) should be reported through CTEP-AERS only if the grade is above the grade provided in the SPEER.

- **Attribution** of the AE:
  - Definite – The AE *is clearly related* to the study treatment.
  - Probable – The AE *is likely related* to the study treatment.
  - Possible – The AE *may be related* to the study treatment.
  - Unlikely – The AE *is doubtfully related* to the study treatment.
  - Unrelated – The AE *is clearly NOT related* to the study treatment.

### 7.3 Expedited Adverse Event Reporting

- 7.3.1 Expedited AE reporting for this study must use CTEP-AERS (CTEP Adverse Event Reporting System), accessed via the CTEP Web site (<https://eapps-ctep.nci.nih.gov/ctepaers>). The reporting procedures to be followed are presented in the “NCI Guidelines for Investigators: Adverse Event Reporting Requirements for DCTD (CTEP and CIP) and DCP INDs and IDEs” which can be downloaded from the CTEP Web site ([http://ctep.cancer.gov/protocolDevelopment/electronic\\_applications/adverse\\_events.htm](http://ctep.cancer.gov/protocolDevelopment/electronic_applications/adverse_events.htm)). These requirements are briefly outlined in the tables below ([Section 7.3.3](#)).

In the rare occurrence when Internet connectivity is lost, a 24-hour notification is to be made to CTEP by telephone at [contact]. Once Internet connectivity is restored, the 24-hour notification phoned in must be entered electronically into CTEP-AERS by the original submitter at the site.

#### 7.3.2 Distribution of Adverse Event Reports

CTEP-AERS is programmed for automatic electronic distribution of reports to the following individuals: Principal Investigator and Adverse Event Coordinator(s) (if applicable) of the Corresponding Organization or Lead Organization, the local treating physician, and the Reporter and Submitter. CTEP-AERS provides a copy feature for other e-mail recipients.

#### 7.3.3 Expedited Reporting Guidelines

Use the NCI protocol number and the protocol-specific patient ID assigned during trial registration on all reports.

**Note: A death on study requires both routine and expedited reporting, regardless of causality. Attribution to treatment or other cause must be provided.**

Death due to progressive disease should be reported as **Grade 5 “Disease Progression”** in the system organ class (SOC) “General disorders and administration site conditions.” Evidence that the death was a manifestation of underlying disease

(e.g., radiological changes suggesting tumor growth or progression; clinical deterioration associated with a disease process) should be submitted.

**Phase 1 and Early Phase 2 Studies: Expedited Reporting Requirements for Adverse Events that Occur on Studies under an IND/IDE within 30 Days of the Last Administration of the Investigational Agent/Intervention**

**FDA REPORTING REQUIREMENTS FOR SERIOUS ADVERSE EVENTS (21 CFR Part 312)**

**NOTE:** Investigators **MUST** immediately report to the sponsor (NCI) **ANY** Serious Adverse Events, whether or not they are considered related to the investigational agent(s)/intervention (21 CFR 312.64)

An adverse event is considered serious if it results in **ANY** of the following outcomes:

- 1) Death
- 2) A life-threatening adverse event
- 3) An adverse event that results in inpatient hospitalization or prolongation of existing hospitalization for ≥ 24 hours
- 4) A persistent or significant incapacity or substantial disruption of the ability to conduct normal life functions
- 5) A congenital anomaly/birth defect.
- 6) Important Medical Events (IME) that may not result in death, be life threatening, or require hospitalization may be considered serious when, based upon medical judgment, they may jeopardize the patient or subject and may require medical or surgical intervention to prevent one of the outcomes listed in this definition. (FDA, 21 CFR 312.32; ICH E2A and ICH E6).

**ALL SERIOUS** adverse events that meet the above criteria **MUST** be immediately reported to the NCI via electronic submission within the timeframes detailed in the table below.

Hospitalization	Grade 1 and Grade 2 Timeframes	Grade 3-5 Timeframes
Resulting in Hospitalization ≥ 24 hrs	10 Calendar Days	24-Hour 5 Calendar Days
Not resulting in Hospitalization ≥ 24 hrs	Not required	

**NOTE:** Protocol specific exceptions to expedited reporting of serious adverse events are found in the Specific Protocol Exceptions to Expedited Reporting (SPEER) portion of the CAEPR.

**Expedited AE reporting timelines are defined as:**

- “24-Hour; 5 Calendar Days” - The AE must initially be submitted electronically within 24 hours of learning of the AE, followed by a complete expedited report within 5 calendar days of the initial 24-hour report.
- “10 Calendar Days” - A complete expedited report on the AE must be submitted electronically within 10 calendar days of learning of the AE.

Serious adverse events that occur more than 30 days after the last administration of investigational agent/intervention and have an attribution of possible, probable, or definite require reporting as follows:

**Expedited 24-hour notification followed by complete report within 5 calendar days for:**

- All Grade 3, 4, and Grade 5 AEs

**Expedited 10 calendar day reports for:**

- Grade 2 AEs resulting in hospitalization or prolongation of hospitalization

For studies using PET or SPECT IND agents, the AE reporting period is limited to 10 radioactive half-lives, rounded UP to the nearest whole day, after the agent/intervention was last administered. Footnote “1” above applies after this reporting period.

Effective Date: May 5, 2011

## 7.4 Routine Adverse Event Reporting

All Adverse Events **must** be reported in routine study data submissions. **AEs reported expeditiously through CTEP-AERS must also be reported in routine study data submissions.**

SAEs requiring submission to the HRPP Office must be reported within 5 calendar days of learning of the event. SAEs not requiring submission to the HRPP Office must be saved in the regulatory binder within 30 calendar days of learning of the event. The report should contain the following information:

The following fields in this section will pre-populate based on the protocol information entered in PIMS.

- IRB Number
- Protocol Title
- Protocol Status
- Sponsoring Department
- Principal Investigator
- Protocol Type
- Protocol Category
- Sponsor

Data needing to be entered:

- The date the adverse event occurred
- The adverse event
- Relationship of the adverse event to the treatment (drug, device, or intervention)
- If the AE was expected
- The severity of the AE
- The intervention
- Detailed text that includes the following
  - An explanation of how the AE was handled
  - A description of the subject's condition
  - Indication if the subject remains on the study
  - If an amendment will need to be made to the protocol and/or consent form.

The PI's signature and the date it was signed are required on the completed report.

## 7.5 Secondary Malignancy

A *secondary malignancy* is a cancer caused by treatment for a previous malignancy (e.g., treatment with investigational agent/intervention, radiation or chemotherapy). A secondary

malignancy is not considered a metastasis of the initial neoplasm.

CTEP requires all secondary malignancies that occur following treatment with an agent under an NCI IND/IDE be reported expeditiously via CTEP-AERS. Three options are available to describe the event:

- Leukemia secondary to oncology chemotherapy (*e.g.*, acute myelocytic leukemia [AML])
- Myelodysplastic syndrome (MDS)
- Treatment-related secondary malignancy

Any malignancy possibly related to cancer treatment (including AML/MDS) should also be reported via the routine reporting mechanisms outlined in each protocol.

## 7.6 Second Malignancy

A second malignancy is one unrelated to the treatment of a prior malignancy (and is **NOT** a metastasis from the initial malignancy). Second malignancies require **ONLY** routine AE reporting unless otherwise specified.

## 8. PHARMACEUTICAL INFORMATION

A list of the adverse events and potential risks associated with the investigational agent administered in this study can be found in Section 7.1.

### 8.1 MLN0128 (TAK-228)

#### 8.1.1 MLN0128 (TAK-228) Drug Information and Availability

**Other Names:** TAK-228, INK128

**Classification:** mTOR inhibitor, TORC1/2

**CAS Registry Number:** 1224844

**Molecular Formula:** C15H15N7O                      **M.W.:** 309.3

**Approximate Solubility:** MLN0128 exhibits a pH-dependant aqueous solubility: at physiological pH the solubility is approximately 0.1 mg/mL and at or below pH 3 the solubility is greater than 15 mg/mL.

**Mode of Action:** MLN0128 is a non-rapamycin analog mTOR (mechanistic target of

rapamycin) kinase inhibitor. The mTOR kinase regulates cell growth, translational control, angiogenesis, and cell survival by integrating nutrient and hormonal signals. The mTOR complex (TORC) is an intracellular point of convergence for a number of cellular signaling pathways. MLN0128 is a potent and selective adenosine tri-phosphate (ATP)-competitive inhibitor of mTOR complex 1 and 2 (TORC1/2).

**Description:** MLN0128 drug substance is a white to off-white, crystalline powder.

**How Supplied:** MLN0128 is supplied by Millennium Pharmaceuticals, Inc. and distributed by the Pharmaceutical Management Branch, CTEP/DCTD/NCI as size 2 hard gelatin capsules in the following strengths: 1 mg (white opaque color) and 3 mg (orange opaque color). The composition of the drug product consists of a blend of MLN0128 drug substance, microcrystalline cellulose, and magnesium stearate. **Milled** formulations will have a white label with a large watermark of the strength on the label.

MLN0128 capsules are packaged in 30-count, 60-cc high-density polyethylene (HDPE), white, opaque, round, tamper- and child-resistant bottles.

**Storage:** Capsules are to be stored in the original package between 15°C to 30°C, with allowed short-term excursions between 2°C and 40°C.

**Route of Administration:** MLN0128 (TAK-228) should be taken on an empty stomach at least 2 hours after food and do not eat or drink (except water) for at least one hour after taking MLN0128 (TAK-228). Do not chew, open or manipulate the capsule in any way prior to swallowing. Each dose should be taken with 8 ounces (240 mL) of water.

**Potential Drug Interactions:** Multiple human metabolizing enzymes are involved in the Phase I metabolism of MLN0128. When normalized for human liver content, the CYP isoforms CYP3A4, CYP2C9, and CYP2C19 appear to contribute to MLN0128 metabolism. MLN0128 displayed low potential ( $IC_{50} > 25 \mu M$ ) for inhibition of the major human CYP isoforms.

**Patient Care Implications:**

Women of childbearing potential should use effective methods of contraception during and through 90 days after the last dose of MLN0128.

Men should use effective methods of contraception and not donate sperm during and through 120 days after the last dose of MLN0128.

8.1.2 MLN0128 (TAK-228) Ordering and Accountability

8.1.2.1 NCI-supplied agents may be requested by the Principal Investigator (or their authorized designee) at each participating institution. Pharmaceutical Management Branch (PMB) policy requires that agent be shipped directly to the institution where the patient is to be treated. PMB does not permit the transfer of agents between

institutions (unless prior approval from PMB is obtained). The CTEP-assigned protocol number must be used for ordering all CTEP-supplied investigational agents. The responsible investigator at each participating institution must be registered with CTEP, DCTD through an annual submission of FDA Form 1572 (Statement of Investigator), Curriculum Vitae, Supplemental Investigator Data Form (IDF), and Financial Disclosure Form (FDF). If there are several participating investigators at one institution, CTEP-supplied investigational agents for the study should be ordered under the name of one lead investigator at that institution.

Active CTEP-registered investigators and investigator-designated shipping designees and ordering designees can submit agent requests through the PMB Online Agent Order Processing (OAOP) application (<https://eapps-ctep.nci.nih.gov/OAOP/pages/login.jsp>). Access to OAOP requires the establishment of a CTEP Identity and Access Management (IAM) account (<https://eapps-ctep.nci.nih.gov/iam/>) and the maintenance of an “active” account status and a “current” password. For questions about drug orders, transfers, returns, or accountability, call [contact] Monday through Friday between 8:30 am and 4:30 pm (ET) or email [[contact]](mailto:[contact]) anytime.

- 8.1.2.2 Agent Inventory Records – The investigator, or a responsible party designated by the investigator, must maintain a careful record of the inventory and disposition of all agents received from DCTD using the NCI Oral Drug Accountability Record Form (DARF). (See the NCI Investigator’s Handbook for Procedures for Drug Accountability and Storage.)

## 9. BIOMARKER, CORRELATIVE, AND SPECIAL STUDIES

### 9.1 Integral Laboratory or Imaging Studies

#### 9.1.1 *NFE2L2, KEAP1 and KRAS mutation assessment*

A detailed explanation of the rationale for targeting *NFE2L2* and *KEAP1* mutations in squamous cell lung cancers and *KRAS* mutant lung cancers harboring *NFE2L2* or *KEAP1* alterations with MLN0128 (TAK-228) can be found in Section 2.0. Briefly, determination of mutation status will be performed through prospective New York State Department of Health approved targeted exon sequencing of patient tumor samples in a CLIA laboratory (IMPACT testing). Results are posted in the patient EMR and discussed in detail by the ordering oncologist. About 70 patients will need to be tested to identify 10 *NFE2L2* mutations. About 140 will need to be tested to identify 10 *KEAP1* mutations, given the restriction in the types of *KEAP1* mutations that are eligible. As of February 2014, 64 patients, predominantly with stage IV disease, have been tested in the past year. We have identified 15 cases with *NFE2L2* mutations and 10 with *KEAP1* mutations. These numbers are in keeping with our anticipated accrual rates for the

protocol.

IMPACT testing will be performed under MSKCC's clinical consent process and *NFE2L2*, *KEAPI*, and *KRAS* mutation results obtained from the medical records.

9.1.1.1 Collection of Specimen(s)

NA

9.1.1.2 Handling of Specimens(s)

NA

9.1.1.3 Shipping of Specimen(s)

N/A

9.1.1.4 Site(s) Performing Correlative Study

Memorial Sloan Kettering Cancer Center

#### 9.2.1.1 Collection of Specimen(s)

Patients will be asked, at the time of initial informed consent to the study, to participate in this optional correlative study which will obtain a biopsy of their tumor before drug dosing and during week 2 (C1D8 +/- 7 days). Patients will have their biopsies snap-frozen in liquid nitrogen and stored in a -80C freezer. A total of up to 4 18-20 gauge needle cores will be obtained, depending on the feasibility as assessed by the physician performing the biopsy. For resection specimens obtained through surgery, a minimum of 0.5 mm^3 of tissue will be obtained.

#### 9.2.1.2 Handling of Specimens(s)

Specimens will be obtained through interventional radiology or surgery. The biopsy will be picked up by the research study assistant and placed immediately in a cryotube and stored in liquid nitrogen.

#### 9.2.1.4 Site(s) Performing Correlative Study

MD Anderson Cancer Center.

## 10. STUDY CALENDAR

*Schedules shown in the Study Calendar below are provided as an example and should be modified as appropriate.*

Baseline evaluations are to be conducted within 2 weeks prior to start of protocol therapy. Informed consent is to be obtained within 45 days prior to start of protocol therapy. Scans and x-rays must be done  $\leq 4$  weeks prior to the start of therapy. Protocol visits, assessments, including radiology assessments must be completed within +/- 7 days. In the event that the patient's condition is deteriorating, laboratory evaluations should be repeated within 48 hours prior to initiation of the next cycle of therapy.

	Pre-Study	Wk 1	Wk 2	Wk 3	Wk 4	Wk 5	Wk 6	Wk 7	Wk 8	Wk 9	Wk 10	Wk 11	Wk 12+	Off Study c
MLN0128 (TAK-228)		A				A				A				
Informed consent	X													
Demographics	X													
Medical history	X													
Concurrent meds	X	X-----X												
Physical exam	X	X		X		X				X				X
Vital signs	X	X		X		X				X				X
Height	X													
Weight	X	X				X				X				X
Performance status	X	X				X				X				X
CBC w/diff, plts	X	X		X		X				X				X
Chemistry a	X	X		X		X				X				X
EKG	X					X								
Adverse event evaluation		X-----X											X	
Tumor measurements	X	Tumor measurements are repeated every 8 weeks. Documentation (radiologic) must be provided for patients removed from study for progressive disease.												X
Radiologic evaluation	X	Radiologic measurements should be performed every 8 weeks.												X
B-HCG	X b													
Optional tumor biopsy	X		X											

A: MLN0128 (TAK-228): Dose as assigned
 
a: Albumin, alkaline phosphatase, total bilirubin, bicarbonate, BUN, calcium, chloride, creatinine, fasting glucose, LDH, phosphorus, potassium, total protein, SGOT [AST], SGPT [ALT], sodium, fasting lipid panel, amylase, lipase
 
b: Serum pregnancy test (women of childbearing potential).
 
c: Off-study evaluation.
 
d: EKGs will be done at screening, pre-dose at week 5 and as needed after week 5
														

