## 6. DOSING DELAYS/DOSE MODIFICATIONS

Toxicities will be graded using the NCI CTCAE Version 4.0 and dose modifications of the study drugs will be made for hematologic and other toxicities. Patients experiencing study drug related toxicities that require a delay in dosing for >21 days will be discontinued from further participation in this study. In the event that patients must have treatment delayed with a treatment cycle due to toxicities, those doses held during a cycle will not be made up.

Dose Level	MLN0128 (TAK-228) Dose
0	3 mg flat dose daily continuous
-1	2 mg flat dose daily continuous
-2	2 mg daily 5 days/ week
-3	1 mg 5 days/week
-4	Withdraw from study

Treatment Modification for MLN0128 (TAK-228)-Related Adverse Events		
Event	CTCAE. V4 Grade	Action to be Taken
QTc prolongation	≥ Grade 3 or > 60ms change from baseline on at least two separate ECGs	
First Occurrence:
 
 
• Omit MLN0128 (TAK-228) dose
 
• Perform an analysis of potassium and magnesium, and if below lower limit of normal, correct with supplements to within normal limits. Concomitant medication usage must be reviewed.
 
• Perform a repeat ECG within one hour of the first QTcF of 500 ms
 
• If QTcF remains > 500 ms, repeat ECG as clinically indicated, but at least once a day until the QTcF returns to < 480 ms. Seek cardiologist input
 
• Once QTcF prolongation has resolved, MLN0128 (TAK-228) may be restarted at a one lower dose level
 
 
Second Occurrence:
 
 
• Permanently discontinue patient from the study treatment
 

	Other Cardiac Events	Grade 1-2
	Grade 3	
Omit dose of MLN0128 (TAK-228) until resolved to ≤ Grade 1
 
 
• If resolved within 7 days, then resume at same dose level of MLN0128 (TAK-228).
 
• If resolved in >7 days, resume at ↓1 dose level of MLN0128 (TAK-228).
 
• If not resolved in 21 days, then discontinue patient from study treatment.
 

	Grade 4	Permanently discontinue patient from the study treatment
Treatment Modification for MLN0128 (TAK-228)-Related Adverse Events		
Event	CTCAE. V4 Grade	Action to be Taken
ENDOCRINE		

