### 7.1 Comprehensive Adverse Events and Potential Risks List (CAEPR) For MLN0128 (TAK-228, NSC 768435)

The Comprehensive Adverse Events and Potential Risks list (CAEPR) provides a single list of reported and/or potential adverse events (AE) associated with an agent using a uniform presentation of events by body system. In addition to the comprehensive list, a subset, the Specific Protocol Exceptions to Expedited Reporting (SPEER), appears in a separate column and is identified with bold and italicized text. This subset of AEs (SPEER) is a list of events that are protocol specific exceptions to expedited reporting to NCI (except as noted below). Refer to the 'CTEP, NCI Guidelines: Adverse Event Reporting Requirements' [http://ctep.cancer.gov/protocolDevelopment/electronic\\_applications/docs/aeguidelines.pdf](http://ctep.cancer.gov/protocolDevelopment/electronic_applications/docs/aeguidelines.pdf) for further clarification. *Frequency is provided based on 390 patients.* Below is the CAEPR for MLN0128 (TAK-228).

**NOTE:** Report AEs on the SPEER **ONLY IF** they exceed the grade noted in parentheses next to the AE in the SPEER. If this CAEPR is part of a combination protocol using multiple investigational agents and has an AE listed on different SPEERs, use the lower of the grades to determine if expedited reporting is required.

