## 7.1.1 CAEPR for MLN0128 (TAK-228)

Version 2.3, July 28, 2019

Adverse Events with Possible Relationship to MLN0128 (TAK-228) (CTCAE 5.0 Term) [n= 390]			Specific Protocol Exceptions to Expedited Reporting (SPEER)
Likely (>20%)	Less Likely (<=20%)	Rare but Serious (<3%)	
BLOOD AND LYMPHATIC SYSTEM DISORDERS			
	Anemia		Anemia (Gr 2)
CARDIAC DISORDERS			
		Cardiac arrest	
		Ventricular fibrillation	
GASTROINTESTINAL DISORDERS			
	Abdominal pain		Abdominal pain (Gr 2)
Constipation			Constipation (Gr 2)
Diarrhea			Diarrhea (Gr 2)
	Dry mouth		Dry mouth (Gr 2)
	Dyspepsia		
Mucositis oral			Mucositis oral (Gr 2)
Nausea			Nausea (Gr 3)
Vomiting			Vomiting (Gr 3)
GENERAL DISORDERS AND ADMINISTRATION SITE CONDITIONS			
	Edema limbs		
Fatigue			Fatigue (Gr 3)
	Fever		Fever (Gr 2)
	General disorders and administration site conditions - Other (mucosal inflammation)		General disorders and administration site conditions - Other (mucosal inflammation) (Gr 2)
INFECTIONS AND INFESTATIONS			
	Urinary tract infection		Urinary tract infection (Gr 2)
INVESTIGATIONS			
	Creatinine increased		Creatinine increased (Gr 2)
		Electrocardiogram QT corrected interval prolonged	
	Platelet count decreased		Platelet count decreased (Gr 2)
	Weight loss		Weight loss (Gr 2)
METABOLISM AND NUTRITION DISORDERS			
Anorexia			Anorexia (Gr 2)
	Dehydration		Dehydration (Gr 2)
Hyperglycemia			Hyperglycemia (Gr 3)
	Hypokalemia		Hypokalemia (Gr 2)
	Hypomagnesemia		Hypomagnesemia (Gr 2)
	Hypophosphatemia		Hypophosphatemia (Gr 2)
MUSCULOSKELETAL AND CONNECTIVE TISSUE DISORDERS			
	Arthralgia		
	Back pain		Back pain (Gr 2)

Adverse Events with Possible Relationship to MLN0128 (TAK-228) (CTCAE 5.0 Term) [n= 390]			Specific Protocol Exceptions to Expedited Reporting (SPEER)
Likely (>20%)	Less Likely (<=20%)	Rare but Serious (<3%)	
	Pain in extremity		
NERVOUS SYSTEM DISORDERS			
	Dizziness		Dizziness (Gr 2)
	Dysgeusia		Dysgeusia (Gr 2)
	Headache		Headache (Gr 2)
PSYCHIATRIC DISORDERS			
	Insomnia		
RENAL AND URINARY DISORDERS			
	Acute kidney injury		
RESPIRATORY, THORACIC AND MEDIASTINAL DISORDERS			
	Cough		Cough (Gr 2)
	Dyspnea		Dyspnea (Gr 2)
	Oropharyngeal pain		
		Pneumonitis	
SKIN AND SUBCUTANEOUS TISSUE DISORDERS			

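### The scheduled chemistry panel omits magnesium, so hypomagnesemia, a listed adverse event with its own reporting grade, may be under-ascertained

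*Combined protocol and SAP*

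**What the plan says.** Section 10, footnote a, spells out the chemistry panel analyte by analyte. It opens with "Albumin, alkaline phosphatase, total bilirubin, bicarbonate, BUN, calcium, chloride" and continues with "creatinine, fasting glucose, LDH, phosphorus, potassium, total protein, SGOT [AST], SGPT [ALT], sodium, fasting lipid panel, amylase, lipase". The calendar marks chemistry at pre-study, weeks 1, 3, 5 and 9, and off study. It is introduced with the words "Schedules shown in the Study Calendar below are provided as an example and should be modified as appropriate".

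The table in Section 7.1.1 is headed "Adverse Events with Possible Relationship to MLN0128 (TAK-228) (CTCAE 5.0 Term) [n= 390" (closing bracket omitted). It puts hypomagnesemia in the Less Likely column (at most 20%). The SPEER entry begins "Hypomagnesemia (Gr 2". Under Section 7.1, events on the SPEER list need expedited reporting only if "they exceed the grade noted in parentheses next to the AE in the SPEER". Section 7.4 requires every adverse event in the routine data submissions, and Section 14 has adverse events tabulated by severity and causality.

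Section 6, in the QTc prolongation row (first occurrence), instructs the site: "Perform an analysis of potassium and magnesium, and if below lower limit of normal, correct with supplements to within normal limits".

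**The concern.** Hypomagnesemia is defined by a laboratory value. Without a measurement it can be neither recognised, unless symptoms prompt a test, nor graded. The plan names it as a possible drug effect and sets a grade above which expedited reporting applies, yet schedules no measurement at any visit.

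Two things are at stake. First, the safety table: if no case appears, a reader cannot tell whether magnesium was normal or was not measured. Second, the timing of the one test the plan does name. Section 6 treats low magnesium as something to check and correct once QTc prolongation is present, but no value is scheduled before that, and the only scheduled on-treatment ECG is at week 5. Section 7.1.1 also lists diarrhea and vomiting as likely (above 20%), and QTc prolongation, ventricular fibrillation and cardiac arrest as rare but serious.

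**Working it through.** The plan states no figure to reproduce here. The check is a comparison of sections, followed by an illustration of size.

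**Step 1. Is magnesium in the panel?** Both parts of footnote a were read item by item. Calcium, potassium, sodium, phosphorus, chloride and bicarbonate are there; magnesium is not. In the text available, the only magnesium test named anywhere is in the QTc row of Section 6. The other mention, in Section 8.1.1, concerns a capsule excipient.

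**Step 2. Is the gap isolated?** The laboratory-defined events in the Section 7.1.1 table, set against the scheduled tests:

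| Event in Section 7.1.1 | SPEER grade | Scheduled test in Section 10 |
|---|---|---|
| Anemia | 2 | CBC |
| Platelet count decreased | 2 | CBC |
| Creatinine increased | 2 | Chemistry (creatinine) |
| Hyperglycemia | 3 | Chemistry (fasting glucose) |
| Hypokalemia | 2 | Chemistry (potassium) |
| Hypophosphatemia | 2 | Chemistry (phosphorus) |
| Hypomagnesemia | 2 | None |

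Six of seven are covered. The panel also includes LDH and lipase, whose elevations Section 7.1.1 places among events with insufficient evidence of a causal link. No reason is given for leaving magnesium out, so an oversight is the likelier explanation.

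**Step 3. Does the QTc rule fill the gap?** Only in part. The test follows prolongation of Grade 3 or higher, or a change above 60 ms, on at least two ECGs. ECGs are scheduled at screening and week 5, then as needed. A patient with low magnesium and no detected QTc event is not tested under this rule.

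**Step 4. Size, as an illustration.**

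- Patients who can still benefit: Section 13.2 gives 20 patients initially accrued, and the planned enrollment table totals 40, so 40 − 20 = 20. This reads the extension as 10 patients in each of cohorts 1 and 2. Section 13.1 already reports response results for 9 + 5 + 5 = 19 patients.
- Rate: the documents give only the upper limit of 20%, for any grade. The lower value of 3% is an assumption. It is suggested by the limit of the rare-but-serious column, but that column also selects on seriousness, so it is not a true floor.
- Expected patients with hypomagnesemia: 20 × 0.03 = 0.6 and 20 × 0.20 = 4.
- Chance of at least one such patient, 1 − (1 − p)^20: at 3%, 1 − 0.97^20 = 0.46; at 20%, 1 − 0.80^20 = 0.99.

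These are counts of patients who would have the event, not of patients in whom it would go undetected. The latter depends on how often magnesium is tested off schedule, which the documents do not give.

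**The case against.** The strongest reply is that the calendar is a minimum. It describes itself as an example open to modification, adverse event evaluation continues throughout treatment, all adverse events must be reported, and nothing prevents a clinician from ordering magnesium. This stands against any claim that cases will certainly be lost. It does not close the gap: permission to modify the calendar tells nobody to add magnesium, and testing that varies by clinician leaves the tabulated rate uninterpretable.

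Four stronger readings that a reader might infer are not supported:

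- *Hypomagnesemia will be missed, and Grade 3–4 cases will go unreported.* Unscheduled testing and the QTc rule can both find cases, and the 20% band is not split by grade, so no number of severe cases can be derived.
- *The QTc rule depends on the scheduled panel.* It orders its own potassium and magnesium test when triggered. That test is reactive, but the rule does not contradict itself.
- *The SPEER entry creates a duty to measure.* It is an exception that limits expedited reporting to higher grades, and does not say which analytes to schedule. The table speaks of a possible relationship, not an established one.
- *The omission exposes patients to a demonstrated QT risk.* Section 2.3 reports a dedicated QT/QTc study, begun after the cardiac death, that found no clinically meaningful electrocardiographic effect.

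Finally, the organ-function criteria in the available text of Section 3.1.7 break off after platelets, so a baseline magnesium criterion there cannot be ruled out. That would not supply on-treatment values.

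**Conclusion.** The point holds as a minor matter of safety ascertainment. Followed as written, the calendar measures six of the seven laboratory-defined events in Section 7.1.1 and does not measure magnesium at any scheduled visit. Hypomagnesemia may therefore be under-ascertained and under-graded, and a zero count would be ambiguous.

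The illustrative size is about 0.6 to 4 of some 20 remaining patients, of any grade. It rests on an assumed range of 3% to 20% and on the extension being 20 patients in all. Applying the same rates to all 40 planned patients gives 1.2 to 8 (40 × 0.03 and 40 × 0.20), and a reader might take that as the number of missed cases. It is neither that nor the number the change could help, since about half the patients were already accrued when the extension was proposed.

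The primary endpoint, the two-stage decision rule and the sample size are not touched.

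**What to change.** Reconcile footnote a in Section 10 with the Section 7.1.1 table and the QTc row in Section 6, and state whether and when magnesium is collected. The simplest way is to add magnesium to footnote a, so that it is run on the chemistry samples already scheduled at pre-study, weeks 1, 3, 5 and 9, and off study. The pre-study sample gives a baseline. Because week 1 is the start of treatment, weeks 3, 5 and 9 and the off-study sample are the ones most able to show a drug effect.

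If magnesium is left out on purpose, give the reason. The safety report should then state how many patients had a magnesium value, so that the hypomagnesemia rate has a usable denominator. For patients treated before the change, the same count should be reported.

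The cost is one line in the calendar, a small assay charge on blood already drawn, and probably a few more low-grade adverse event entries. No treatment, dosing or supplementation rule is proposed.
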